## **5.1. Analysis Specifications**

### **5.1.1. Level of Significance**

In general, a two-sided significance level of  $\alpha = 0.05$  will be used for all hypothesis testing and all CIs will be calculated on the two-sided 95% confidence level, unless otherwise specified.

### **5.1.2. Data Handling Rules**

In general, no imputation method is planned for handling missing or incomplete data. Sensitivity analyses with censoring rules may be conducted if warranted and will be documented in the clinical study report.

## **5.2. Primary Endpoints**

### **5.2.1. Dual-Primary Endpoint of rPFS**

#### **5.2.1.1. Definition**

The dual-primary efficacy endpoint is radiographic progression-free survival (rPFS), as assessed by the investigator, and is defined as the duration from the date of randomization to the date of first documentation of radiographic progressive disease or death due to any cause, whichever occurs first. Radiographic progression will be assessed by soft tissue lesion by computed tomography (CT) or magnetic resonance imaging (MRI) per modified RECIST 1.1 or by bone lesion progression on bone scan.

### 5.2.1.2. Censoring Rules

Subjects that withdraw from the study (i.e., withdrawal of consent, lost to follow-up) or receive selected new systemic anti-cancer therapy without documented disease progression will be censored on the date of the last tumor assessment. Subjects with no evidence of radiographic progressive disease or death will be censored on the date of the last tumor assessment. If there was no tumor assessment performed after the baseline visit, the subject will be censored on the date of randomization. Censoring rules are summarized as shown in [Table 2](#).

**Table 2: Censoring Rules**

Scenario	Censoring rule
No tumor assessment at Baseline or No tumor assessment after Baseline	Censored on the date of randomization
Subjects who are lost to follow-up or withdraw from study	Censored on the date of the last tumor assessment
Subjects who receive selected new systemic anti-cancer therapy prior to documented disease progression or death	Censored on the date of the last tumor assessment prior to the start of the new systemic anti-cancer therapy or death
Subjects with no evidence of radiographic progressive disease or death	Censored on the date of the last tumor assessment
Subjects with 2 or more consecutive missing assessments followed by evidence of radiographic progressive disease or death	Censored on the date of the last tumor assessment before the missing assessments.

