	Notes	28 days before randomization, unless otherwise specified	C1D1	D1 of C2 to C13, then D1 of q2 cycles to C25, then D1 of q4 cycles until EOT, unless otherwise specified	EOT Visit	q4 months
Study treatment should be initiated (C1D1) within 3 calendar days after randomization. Each treatment cycle is 28 days. During the Treatment Phase, study visits may occur within \pm 2 day window (for CT/MRI and bone scans, see below). The EOT visit must occur within 30 days after the last dose of study drug. Follow-up will continue until death, lost to follow-up, withdrawal of consent, or study termination.						
Screening						
Informed consent	ICF must be signed before any study-related procedures.	X				
Inclusion/exclusion criteria		X				
Prestudy anti-cancer therapy, palliative radiation, or surgical therapy		X				
Demography/Medical history		X				
Gleason score at diagnosis		X				
Study Drug Administration						
Dosing compliance and dispense study drug	See Section 7, Treatment Compliance; Only compliance at the EOT Visit (no drug dispensing)		X	X	X	
Administer study drug JNJ-56021927 (apalutamide)/placebo	240 mg once daily on 28-day treatment cycles, see Section 6.1		<-----Continuous dosing----->			
Safety						
Electrocardiogram, 12-lead	See Section 9.6, Electrocardiograms	X				
Physical examination	See Section 9.6, Physical Examination	X		X	X	
Vital signs	After Screening Phase, only blood pressure; see also Section 9.6, Vital Signs	X		X	X	
ECOG PS		X		X	X	

		Screening Phase	Treatment Phase			Follow-up Phase
	Notes	28 days before randomization, unless otherwise specified	C1D1	D1 of C2 to C13, then D1 of q2 cycles to C25, then D1 of q4 cycles until EOT, unless otherwise specified	EOT Visit	q4 months
Efficacy						
CT or MRI (chest, abdomen, and pelvis)	Visits for ^{99m} Tc bone scans or CT/MRI may occur up to 8 days before cycles requiring images. Unscheduled assessments can occur at any time as needed if signs of disease progression are observed. See Sections 9.2.1, 9.2.2, and 9.2.3.	Within 6 weeks prior to randomization		C3, C5, then q4 cycles	Not needed if previously done ≤6 weeks	
^{99m} Tc Bone Scan						
Medical Resource Utilization	See Section 9.5		Continuous			
ePROs: For cycles with an on-site visit, complete before any tests, procedures or other consultations for that visit. For non-visit cycles and during the Follow-up Phase, the questionnaires are completed remotely.						

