### 2.1. Visit Windows

The Treatment Phase will begin at Cycle 1 Day 1 of treatment and will continue until study drug is discontinued. Study treatment should be initiated (Cycle 1 Day 1) within 3 calendar days after randomization. Visits for each cycle will have a  $\pm 2$  day window except for computed tomography (CT)/magnetic resonance imaging (MRI) and bone scans (imaging visits may occur up to 8 days before scheduled cycles).

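### The rPFS rule that censors at randomization anyone without a post-baseline scan does not except deaths, although death is an rPFS event; PFS2 censoring has the same gap

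*SAP*

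**What the plan says.** SAP 5.2.1.1 defines rPFS as time from randomization to "radiographic progressive disease or death due to any cause, whichever occurs first". Protocol 9.2.3 agrees.

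SAP 5.2.1.2 then states: "If there was no tumor assessment performed after the baseline visit, the subject will be censored on the date of randomization". Table 2 summarises the censoring rules in five rows, numbered here from the top:

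- Row 1, "No tumor assessment at Baseline or No tumor assessment after Baseline": censored at randomization. Death is not mentioned.
- Row 2, lost to follow-up or withdrawn: censored at the last tumor assessment. Death is not mentioned.
- Row 3, "Subjects who receive selected new systemic anti-cancer therapy prior to documented disease progression or death": censored at the last assessment before the trigger.
- Row 4, "Subjects with no evidence of radiographic progressive disease or death": censored at the last assessment. Men who died are outside this row.
- Row 5, "Subjects with 2 or more consecutive missing assessments followed by evidence of radiographic progressive disease or death": censored at the last assessment before the gap. Here a death is censored on purpose.

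The SAP gives no order of precedence among the rows. Protocol 11.3 limits censoring to subjects without an event, but leaves the detailed rules to the SAP.

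For PFS2, SAP Table 3 counts progression on the first subsequent therapy or death. One censoring sentence covers subjects with no progression on that therapy, and the other covers subjects not on subsequent therapy. Neither is limited to men who are alive. By contrast, the OS rule in SAP 5.2.2 is limited to the living. The rule for prostate cancer-specific survival in Table 3 treats living men and deaths from other causes separately.

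**The concern.** A man with a baseline scan who dies on day 40 has had no post-baseline scan and has not missed two scheduled assessments. By SAP 5.2.1.1 he is an event on day 40. By row 1 he is censored on day 0 and contributes nothing. Two programmers who both follow the SAP could code him differently, in a dual-primary endpoint tested at a two-sided 0.005. Neither can simply assume that death overrides every censoring row, because row 5 shows that the SAP does censor some deaths.

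If the coding were settled only after the data are unblinded, the choice would depend on the data and would concern the earliest deaths.

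For PFS2 the literal reading goes further. The two sentences together cover every man without progression on a first subsequent therapy. A death after such progression is not the first event. Read literally, the death component of PFS2 would have almost no effect.

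**Working it through.** **The plan's own figure.** SAP 1.4 gives 368 rPFS events, HR 0.67, two-sided alpha 0.005, power at least 85%. The Schoenfeld formula gives 4 × (2.807 + 1.036)² / (ln 0.67)² = 369 events, so 368 is reproduced. Power = Φ(√(D/4) × |ln HR| − 2.807), which at D = 368 is 0.849 for HR 0.67. At the plan's medians of 20 versus 30 months (HR 0.667) it is 0.860.

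**When the first scheduled scan falls.** The Protocol Time and Events Schedule places it at Cycle 3. Cycle 3 Day 1 is 2 × 28 = 56 days after Cycle 1 Day 1, which is 0 to 3 days after randomization. SAP 2.1 says that "imaging visits may occur up to 8 days before" the scheduled cycle. The range is 56 − 8 = day 48 to 56 + 3 = day 59.

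**Deaths before that scan.** Inputs from SAP 1.4: control median OS 44 months, HR 0.75, about 1,000 subjects, hence 500 per arm at 1:1. Assumed: constant hazard and a month of 30.4375 days. Control hazard is ln 2/44 per month and the apalutamide hazard is 0.75 times that. Deaths per arm = 500 × (1 − exp(−hazard × t)).

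| Day | Control | Apalutamide | Total | Share of 368 |
|---|---|---|---|---|
| 48 | 12.3 | 9.2 | 21.5 | 5.8% |
| 59 | 15.0 | 11.3 | 26.4 | 7.2% |

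This also assumes that none of these men had an unscheduled scan. If early mortality were 25 to 50% of the planning rate (an assumption), the total would be about 5 to 13.

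Men who miss the Cycle 3 scan and die before Cycle 5 would add a little. About 24 deaths fall between the two scans, so 1 to 2 more if 5 to 10% of those men missed Cycle 3 (an assumption).

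**Power if these events were lost and not replaced, HR 0.67.**

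| Events lost | D | Power |
|---|---|---|
| 0 | 368 | 0.849 |
| 5 | 363 | 0.843 |
| 13 | 355 | 0.833 |
| 21 | 347 | 0.822 |
| 26 | 342 | 0.815 |

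At 20 versus 30 months, power goes from 0.860 to 0.827 at D = 342. If the analysis waits for 368 events, no power is lost. The documents point both ways on this. Protocol 11.3.2 ties the final rPFS analysis to the first OS interim at about 205 deaths, while SAP 5.2.1.4 refers to reaching a prespecified number of rPFS events.

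**Where rows 1 and 5 overlap.** Take a man with no post-baseline scan who misses two scheduled assessments and then dies. Both rows censor him, but on different dates. Row 1 gives randomization. Row 5 gives the last scan before the gap, which is the baseline scan. The Protocol schedule allows that scan "Within 6 weeks prior to randomization", so the censoring date could precede randomization by up to 42 days.

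**PFS2.** No size can be computed. The documents do not give the share of deaths that occur without progression on a first subsequent therapy.

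**The case against.** The strongest reply is that the text largely resolves itself. In SAP 5.2.1.2 the no-scan sentence directly follows the one on subjects with neither progression nor death. Its natural role is to supply a date for that event-free subject when no later scan exists. Protocol 11.3 censors only subjects without an event. For PFS2, a reading that empties the definition is one few programmers would adopt. This stands as evidence of intent. It does not remove the conflict: row 1 lacks the limit that row 4 carries, and the protocol hands the detailed rules to the SAP, where the conflict sits.

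The second reply is that 21 to 26 deaths is too many. Entry requires ECOG grade 0 or 1 and excludes recent serious cardiac disease and poor laboratory values. Unscheduled imaging is provided for, Protocol 10.2 asks for imaging at treatment discontinuation, and deaths already censored under rows 2 and 3 are not subtracted. This is right, and the figure should be read as an upper bound on deaths before the first scheduled scan. The part of row 1 on missing baseline scans should concern almost no one, because a positive bone scan is an entry criterion.

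A reader might infer that the plan drops early deaths from rPFS, or that the rPFS result would be biased. The documents do not support either. No passage says that such deaths are to be excluded, and nothing above shows bias or an inflated type I error. The same deaths count in OS under any reading.

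**Conclusion.** The contradiction is real and lies in a dual-primary endpoint, but its consequence is modest. As written, the no-scan rule gives the wrong result for a death before the first scan, while the context suggests that the death is meant to count. It should be settled before unblinding.

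The exposure is at most about 21 to 26 events (6 to 7% of 368), assuming the SAP's OS medians, constant hazard from randomization and no unscheduled scans. The true number is probably much smaller. The worst-case power is about 0.815 at HR 0.67, or 0.827 at 20 versus 30 months, and only if the lost events are not replaced.

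The PFS2 omission is the same in kind and wider in literal scope. It affects an endpoint listed under other endpoints, and its size and direction cannot be computed from the documents.

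**What to change.** 1. Limit Table 2 row 1 and the no-scan sentence in SAP 5.2.1.2 to subjects with neither documented radiographic progression nor death. State that a death before any post-baseline scan is an rPFS event on the date of death unless row 2, 3 or 5 applies. This leaves the sponsor's choices in those rows untouched.
2. State that where row 5 applies and there is no post-baseline scan, the censoring date is randomization. The same date should be named for rows 2 and 3, where the question arises once row 1 no longer covers men who died.
3. For PFS2 in SAP Table 3, limit both censoring sentences to subjects alive, and state that death is an event whether or not subsequent therapy was started. The sponsor should also name the censoring date for men alive who never started a subsequent therapy. The present sentence does not say which progression it refers to, and progression on a therapy never started cannot supply a date.

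A sensitivity analysis that counts all deaths as rPFS events is optional. SAP 5.1.2 already allows analyses under other censoring rules if warranted.

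The cost is a few words in three places. Death dates, scan dates and first subsequent therapy are already collected, and alpha, sample size and conduct do not change.

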### 5.2.1.3. Analysis Methods

The primary analysis for the comparison of the rPFS distributions between the two treatment groups will be carried out using the stratified log rank test at a two-sided significance level of 0.005. At the time of primary analysis of rPFS it is projected that approximately 50% of the total number of required events for the OS analysis will be observed. Stratified Cox proportional-hazard model will be used to obtain the HR and its 95% confidence interval. Non-stratified log rank test will be performed as a sensitivity analysis.

To assess the consistency of treatment benefit with respect to the primary efficacy endpoint of rPFS across important subgroups, forest plots will be provided for subgroups as defined in [Section 2.4](#). The comparison between the two treatment groups will be evaluated using the hazard ratio with its 95% CI from a univariate Cox regression model in each subgroup. There is no planned interim analysis on rPFS. Additional rPFS subgroup analyses on subjects with low- or high-volume mHSPC disease may be performed as an update at the time of subsequent OS analysis without alpha spending assigned.

Multivariate Cox regression analysis, adjusting for important selected prognostic factors, will also be performed as supportive analysis, if appropriate. The adjusted hazard ratio and its 95% confidence interval for treatment and each factor will be provided. The following baseline covariates will be considered for inclusion in the model:

- PSA
- Lactate dehydrogenase
- Alkaline phosphatase
- Hemoglobin
- Pain at baseline
- Age
- ECOG PS grade (0 vs. 1)
- Number of bone lesions at baseline ( $\leq 10$  vs.  $>10$ )
- Presence of visceral disease (yes vs. no)
- Receipt of localized therapy (yes vs. no)

- Geographic region (NA/EU vs. other countries)
- Gleason score ( $\leq 7$  vs.  $>7$ )
- Prior docetaxel use (yes vs. no)

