2. OBJECTIVES AND HYPOTHESIS

2.1. Objectives

Primary Objective

The primary objective is to determine if the addition of apalutamide to ADT provides superior efficacy in improving radiographic progression-free survival (rPFS) or OS for subjects with mHSPC.

Secondary Objectives

- To evaluate clinically relevant improvements with addition of apalutamide to ADT including delays in pain progression and opioid use for prostate cancer, skeletal-related events (SREs), and the need for cytotoxic chemotherapy
- To characterize the safety of adding apalutamide to ADT in subjects with mHSPC
- To characterize the population pharmacokinetics (PK) and pharmacodynamics (PD) of apalutamide
- To evaluate the concentration of leuprolide and assess the PD effect of leuprolide on testosterone concentrations when used alone or in combination with apalutamide
- To evaluate the treatment effectiveness with the addition of apalutamide to ADT for the subpopulations of subjects with low-volume or high-volume mHSPC

Other Objectives

- To evaluate exploratory biomarkers predictive of response and resistance to treatment
- To evaluate patient relevant outcomes including symptoms (ie, pain, fatigue, urination) and function (ie, physical, emotional, social) and health-related quality of life
- To evaluate improvements in other clinically relevant endpoints with the addition of apalutamide to ADT
- To collect medical resource utilization (MRU) data that may be used in future economic modeling (the construction and reporting of the economic model will be conducted separately from this study)

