## 2.4. Definition of Subgroups

In order to assess the consistency of treatment benefit with respect to the dual-primary efficacy endpoints of rPFS and OS, univariate analyses will be performed for the following important subgroups:

- Baseline Eastern Cooperative Oncology Group (ECOG) performance status (PS) grade (0; 1)
- Geographic region (EU and NA; Other Countries)
- Bone metastasis only at baseline (yes; no)
- Visceral disease at baseline (yes; no)
- Gleason Score at diagnosis ( $\leq 7$ ;  $> 7$ )
- Prior docetaxel use (yes; no)
- Age ( $< 65$ ;  $\geq 65$ ;  $\geq 75$ )
- Baseline PSA above median (yes; no)
- Baseline LDH above upper limit normal (yes; no)
- Baseline ALP above upper limit normal (yes; no)
- mHSPC (high volume; low volume)
- Number of bone lesions ( $\leq 10$ ,  $> 10$ )

High-volume mHSPC is based on an adaptation of the CHAARTED study and is defined as 1) visceral metastases and at least 1 bone lesion or 2) at least 4 bone lesions, with at least 1 bone lesion outside of the vertebral column or pelvis (see also Section 1.2). Low-volume mHSPC is defined as the presence of bone lesion(s) not meeting the definition of high-volume mHSPC.

Subgroup analysis of a country may be conducted for filing purpose.

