#### 5.2.2. Dual-Primary Endpoint of OS

The efficacy endpoint of OS is defined as the time from date of randomization to date of death from any cause. Subjects alive at time of analysis will be censored on the last date the subject was known to be alive.

The primary analysis for the comparison of the OS distributions between the two treatment groups will be carried out using the stratified log rank test at a two-sided significance level of 0.045. The analysis methods for OS will be similar to those outlined for the analysis of rPFS (see Section 5.2.1.3). In addition, 2-year, 3-year survival rates will be estimated using the Kaplan-Meier method. Subgroup analyses on subjects with low- or high-volume mHSPC disease will be performed without alpha spending assigned.

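### Consistency of benefit across subgroups, including disease volume, rests on separate hazard ratios; no estimate of the difference between subgroups is planned for rPFS or OS

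*SAP*

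**What the plan says.** SAP 2.4 gives the purpose of the subgroup work: "In order to assess the consistency of treatment benefit with respect to the dual-primary efficacy endpoints of rPFS and OS, univariate analyses will be performed". High versus low volume is one of the twelve subgroup factors listed there. SAP 5.2.1.3 repeats the purpose for rPFS ("To assess the consistency of treatment benefit with respect to the primary efficacy endpoint of rPFS across important subgroups, forest plots will be provided") and names the method: "The comparison between the two treatment groups will be evaluated using the hazard ratio with its 95% CI from a univariate Cox regression model", one model per subgroup. For OS, SAP 5.2.2 says: "The analysis methods for OS will be similar to those outlined for the analysis of rPFS". It adds: "Subgroup analyses on subjects with low- or high-volume mHSPC disease will be performed without alpha spending assigned".

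Disease volume also appears as a secondary objective in Protocol 2.1 and SAP 1.1.2: "To evaluate the treatment effectiveness with the addition of apalutamide to ADT for the subpopulations of subjects with low-volume or high-volume mHSPC".

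Neither document mentions a treatment-by-subgroup interaction term, a ratio of hazard ratios or any other between-subgroup estimate. The multivariate Cox model in SAP 5.2.1.3 lists baseline covariates, and volume is not among them. Volume is not a stratification factor either. SAP Attachment 1 has a similar consistency aim for high-risk and low-risk subjects, and it offers only Kaplan-Meier estimates and descriptive summaries.

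**The concern.** Consistency is a statement about the difference between subgroups. A Cox model containing treatment alone, fitted inside one subgroup, does not estimate that difference. A reader of the forest plot sees a set of intervals whose widths depend mainly on event counts, and can easily take a difference in precision for a difference in effect.

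Volume is where this matters most. Protocol 1.2 reports that treatment guidance already separates low-volume from high-volume disease, so readers will look for a volume-specific conclusion. If low-volume subjects contribute fewer events, their interval may well cross 1 when the high-volume interval does not, even if the drug works equally well in both. The trial could then be quoted as showing benefit in high-volume disease only. If there were a real difference, the report would contain no planned estimate of its size.

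**Working it through.** **Inputs from the documents.** rPFS: 368 events, HR 0.67, two-sided 0.005, at least 85% power. OS: 410 deaths, HR 0.75, two-sided 0.045, about 80% power (SAP 1.4). OS looks at about 205 and 287 deaths (SAP 3.1). Allocation 1:1.

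**Assumed.** The low-volume share of events is not given for this trial. I use 20% to 34.2%. The upper end is the low-volume share of patients in the docetaxel trial cited in Protocol 1.2 (1 − 520/790 = 34.2%), taken as if events were proportional to patients. The lower end allows for better prognosis in low-volume disease.

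**The plan's own figures.**
- rPFS events: 4 × (2.807 + 1.036)² / (ln 0.67)² = 59.09 / 0.1604 = 368.4, against 368 in the plan.
- OS power at 410 deaths, fixed design: Φ(0.2877 × √410 / 2 − 2.005) = Φ(0.908) = 81.8%. With two interim looks, simulation using the cumulative alpha spends in the Amendment 4 change log (0.0091 and 0.0224) gives 80.0%.

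Both agree with the plan.

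**Subgroup intervals.** With d events, SE(ln HR) = 2/√d. If the true HR is the same in both groups, P(95% CI includes 1) = 1 − Φ(|ln HR| × √d / 2 − 1.96). For rPFS at a 20% share, d = 0.20 × 368 = 73.6 and |ln HR| × √d / 2 = 0.4005 × 8.579 / 2 = 1.718, so the probability is 1 − Φ(−0.242) = 0.596. The two volume groups share no subjects, so the chance of the split pattern (high-volume CI excludes 1, low-volume CI does not) is the product of the two separate probabilities.

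| Analysis | Low-volume events (34.2% to 20%) | Low-volume CI includes 1 | High-volume CI excludes 1 | Split pattern |
|---|---|---|---|---|
| rPFS, 368 events | 126 to 74 | 39% to 60% | 88% to 93% | 34% to 55% |
| OS, 205 deaths | 70 to 41 | 78% to 85% | 39% to 45% | 30% to 39% |
| OS, 287 deaths | 98 to 57 | 70% to 81% | 51% to 59% | 36% to 47% |
| OS, 410 deaths | 140 to 82 | 60% to 75% | 66% to 74% | 40% to 55% |

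If instead 35–60 of the first 205 deaths are assumed to be low-volume, the split pattern arises in 40% down to 33% of trials.

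**Even-odds point.** The interval includes 1 half the time when d = 4 × 1.96² / (ln HR)². That is 96 events for rPFS (26% of 368) and 186 deaths for OS (91%, 65% and 45% of 205, 287 and 410).

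**Projected rPFS share.** Protocol 1.2 quotes pooled OS medians by risk group from another docetaxel trial: 69.1, 46.5 and 36.6 months. These imply hazard ratios, low-risk versus the others, of 46.5/69.1 = 0.67 and 36.6/69.1 = 0.53. Taking 33–34% low-volume patients, those ratios, exponential survival and uniform 30-month accrual puts the low-volume share of rPFS events at 23–28%, and the chance that its CI includes 1 at 47–54%. These are proxies by risk group, not by volume.

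**The missing estimate.** The SE of the log ratio of HRs is √(4/d_low + 4/d_high). For rPFS at a 20% share this is √(4/73.6 + 4/294.4) = 0.261, so the 95% CI is the estimate multiplied and divided by exp(1.96 × 0.261) = 1.67. At 34.2% the factor is 1.54. For OS it is 1.78 to 1.98 at 205 deaths and 1.50 to 1.62 at 410. With identical effects, this interval excludes 1 in 5% of trials. If low-volume HR were 1 and high-volume HR the design value, it would exclude 1 in 34–45% of trials for rPFS and 21–28% for OS at 410 deaths.

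**The case against.** The case on the other side is substantial.

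- **No decision rule.** A reader might infer that the SAP judges a subgroup by whether its interval excludes 1. It does not say so; it plans a forest plot, which can be read by comparing each HR with the overall HR, and the volume analyses carry no alpha. This stands. The harm is a foreseeable misreading, not a planned wrong inference.
- **rPFS differs from OS.** A reader might infer that low-volume disease would usually look unproven on both endpoints. For rPFS the chance is about even, and exceeds one half only if low-volume subjects supply fewer than about 26% of events.
- **The first OS look is immature for everyone.** At 205 deaths with a true HR of 0.75, the interval for the whole ITT population includes 1 in 46% of trials. With 35–60 low-volume deaths, the high-volume interval includes 1 in 53–59%. The high low-volume figure at that look is therefore mostly a matter of few deaths.
- **The volume objective.** A reader might take it to require a high-versus-low comparison. Its wording asks for the effect within each subpopulation, which separate HRs answer. The mismatch comes from the consistency aim in SAP 2.4 and 5.2.1.3.
- **The ratio can be derived by hand, and is imprecise.** Because the groups are disjoint, anyone can divide the two HRs and combine the standard errors. So the difference is left unreported rather than made inestimable. Neither point is a reason to leave it out: a wide interval shows plainly that the data cannot separate the groups.

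**Conclusion.** The point holds as a gap between aim and method. The SAP wants to assess consistency across subgroups and plans no quantity that measures it, for rPFS or OS. With identical true effects and an assumed 20–34% low-volume share of events, the low-volume CI would cross 1 in about 39–60% of trials for rPFS, and in 60–85% for OS across the three looks. The pattern most likely to mislead would arise in about 34–55% of trials for rPFS, about 33–40% for OS at 205 deaths (35–60 low-volume deaths assumed) and 40–55% at 410.

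All of this depends on the assumed share and on equal true HRs at the design values. The OS conclusion is stable over the range shown; the rPFS one is not. The documents do not support saying that the SAP will declare low-volume benefit unproven. The primary tests and the alpha plan are untouched, so this is a low-severity improvement to reporting.

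**What to change.** In SAP 5.2.1.3, and by reference 5.2.2, add for rPFS and OS a Cox model with treatment, volume and treatment-by-volume terms. Report the ratio of HRs (high versus low) with its 95% CI beside the two subgroup HRs on the forest plot. State that it is a descriptive estimate with no alpha and is not a pass/fail test, because its power is low and a CI that includes 1 does not establish consistency. The same estimate can be shown descriptively for the other subgroups in SAP 2.4.

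The cost is one more model per subgroup on data already collected. The downsides are wide intervals and, if extended to all the listed subgroups, a column of imprecise estimates with no multiplicity control, which the text should say.
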